### B.1 Sample

Participants for Aim 1, Phase 1 studies will be young adults (age 18-35 years) who live in the United States and are susceptible to multiple nicotine and tobacco product use (i.e., have used combustible tobacco or e-cigarettes at least once).

In the Aim 1 Phase 1 focus groups and interviews, participants expressed concern that relative risk messages comparing combustible cigarette and ENDS use could increase young adult non-users' curiosity and intentions to use ENDS. The goal of anti-tobacco messages being tested in this study is to increase harm perceptions and decrease use intentions among susceptible nicotine and tobacco users. However, we also do not want to negatively impact nonusers. After conferring with the mentoring committee and scientific experts, in Phase 2, we will address this concern by empirically testing whether responses to absolute and relative risk messages vary by nicotine and tobacco user type. As such, our sample will include young adults (age 18-35 years) who live in the United States. Per the Aim 1, Phase 1 studies, half of our sample will include young adults who are susceptible to multiple nicotine and tobacco product use (i.e., have used combustible tobacco or e-cigarettes at least once) and half of the sample will comprise U.S. young adult nonusers.

For Aim 1, Phase 1, Study 1--FOCUS GROUPS: The maximum overall sample size will be N = 58. However, our analytic sample size will start with 3 focus groups of size 6-8 individuals (N = 18-24 total participants). This sample size is standard in "usability research," where existing messages are tested to uncover issues of effectiveness, and newly designed prototypes are tested to improve any communication issues. *If we do not reach thematic saturation, we will conduct additional focus groups until thematic saturation is achieved, up to a total analytic sample size of N = 48 participants.* We have inflated the overall sample size to 29 participants for each round of focus groups (N = 58) to allow for 20% dropout.

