### **B. Aim 1, Phase 1: Study 2-ONLINE RATING SURVEY Data Analysis**

For online rating survey data, we will describe mean and median values of participants' ratings of perceived message effectiveness, likeability, and reactance.

In exploratory analyses, we will assess whether there are systematic differences in participants' ratings by message type (AR vs RR), gender, LGBT status (vs non-LGBT), race/ethnicity, age (e.g., 18-24 vs 25-35) and tobacco user type (e.g., current, former, never polytobacco user). We will test mean differences between groups using t-tests or ANOVA. If there are violations of assumptions (e.g., normality) we will test median differences between groups using Wilcoxon rank-sum test (two groups) or Kruskal Wallis test (more than 2 groups).

We will also run exploratory regression models to evaluate the effect of risk message type (e.g., absolute risk vs. relative risk) and efficacy message type (e.g., quit; switch; combination) on messages on perceived message effectiveness, likeability, and reactance; controlling for pro- and anti-tobacco marketing exposure, baseline risk and efficacy perceptions and behavioral intentions. For models testing the effect of efficacy

messages, we will conduct overall F-tests to determine if there is an effect of efficacy message type in each model. If so, pairwise t-tests will be conducted, and Holm's procedure will be used to control Type I error rate.

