#### **D. Aim 1, Phase 2: ONLINE FACTORIAL EXPERIMENT (NCT05393869) Data Analysis**

We will fit linear regression models to evaluate the effect of condition on perceived effectiveness, risk perceptions, and behavioral intentions. Covariates will include exposure to pro- and anti-tobacco marketing, and baseline risk perception and behavioral intention items (per respective models). Baseline and post-viewing scores may be transformed if violations of assumptions are detected. We will conduct overall F-tests to determine if there is an effect of condition in each model. If so, pairwise t-tests will be conducted, and Holm's procedure will be used to control Type I error rate. Exploratory analyses will be conducted to determine if there is an interactive effect between Condition x Topic. *Responses will be examined by gender and sexual orientation to determine if there are systematic differences.*

Sample Size Justification: For the Aim 1, Phase 2: ONLINE FACTORIAL EXPERIMENT

(NCT05393869) an analytic sample size of 400 participants per group will allow us to detect the best message in terms of risk perception score with 75% probability assuming the mean score in the best group is at least 0.1 standard deviations better than the mean score in the second best group. As effect sizes of 2 or greater are reported in the literature for this outcome, we do not consider smaller differences to be of interest. As our analytic sample size is N = 2800 participants (n = 400 participants per experimental or control group); we have inflated our overall sample size is inflated by 5% to account for estimated inconsistencies between prescreening and survey responses, resulting in an overall sample size of N = 2940.

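### The Phase 2 analysis plan has no term for the user-type comparison that half of its sample was recruited to support

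*Combined protocol and SAP*

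**What the plan says.** Section B.1 (Sample) reports that Phase 1 participants worried that messages comparing cigarettes with ENDS could make nonusers more curious about ENDS and more inclined to use them. The protocol responds that "we also do not want to negatively impact nonusers". It commits Phase 2 to "empirically testing whether responses to absolute and relative risk messages vary by nicotine and tobacco user type" and accordingly sets that "half of the sample will comprise U.S. young adult nonusers"; the other half are people who have used combustible tobacco or e-cigarettes at least once.

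Section VI.D, the Phase 2 analysis, fits linear regressions of perceived effectiveness, risk perceptions and behavioral intentions on condition. Covariates are marketing exposure and the relevant baseline items. Testing then runs: "We will conduct overall F-tests to determine if there is an effect of condition in each model. If so, pairwise t-tests will be conducted", with Holm adjustment. The only effect modifiers named are message topic (an exploratory interaction with condition) and two demographic factors: "Responses will be examined by gender and sexual orientation to determine if there are systematic differences".

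Three other places bear on the point:

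- The III.B overview of Phase 2 still describes the sample as young adults who have ever been polytobacco users, which does not match B.1.
- The analysis of the Phase 1 rating survey (VI.B) does list tobacco user type, among exploratory comparisons, but that is a different study.
- The first Aim 1 hypothesis (section I) is about a factor: RR against AR messages, with risk perceptions as the outcome.

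**The concern.** The user-type question determined who makes up half the sample, and it concerns possible harm to people who do not use tobacco. The plan names no model, contrast or outcome for it. Anything later reported by user type would therefore have been chosen without a stated rule, and a report that followed VI.D to the letter would not address the question at all.

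Pooling also causes a problem of interpretation. Intentions to quit all tobacco or to switch to ENDS have no clear meaning for someone who uses neither, yet VI.D models behavioral intentions across the whole sample.

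A lesser matter concerns the RR-versus-AR hypothesis. Section IV.D uses condition for a cell of the 2x3 design. VI.D therefore reaches the threat factor only through an omnibus test, which does not isolate it, and then through comparisons of individual cells.

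**Working it through.** **The plan's own figure.** VI.D justifies 400 per group by a 75% chance of picking the best group when the "mean score in the best group is at least 0.1 standard deviations better than the mean score in the second best group". The probability of correct selection is the integral of Φ(x + 0.1√400)^(k−1) φ(x) dx. It gives 75.9% for k = 6 and 73.3% for k = 7, so the stated 75% is reproduced. The total also follows: 7 × 400 = 2800, and 2800 × 1.05 = 2940. This calculation is about selection. It covers neither the user-type interaction nor the RR-versus-AR contrast.

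**Assumptions.** SD 1, two-sided 0.05 (VI.D gives no alpha), seven groups of 400 (three AR, three RR, one control), each half users and half nonusers, and no covariate gain unless stated. Power is Φ(d/SE − 1.96).

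**Dilution.** With a 50/50 split, an RR effect of 0.20 SD in nonusers and none in users averages to 0.5 × 0.20 + 0.5 × 0 = 0.10 SD.

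**Threat by user status.** Each of the four threat-by-status cells holds 3 × 200 = 600. SE = √(4/600) = 0.0816. Power at a difference in effects of 0.10/0.20/0.30 SD is 23/69/96%; 80% power needs about 0.23 SD. The gain from baseline covariates is not in the documents. If their correlation with the outcome is 0.5, the SE becomes 0.0707 and power 29/81/99%; at 0.7, the SE is 0.0583 and power 40/93/>99%.

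**RR versus control in nonusers.** 600 against 200: SE = √(1/600 + 1/200) = 0.0816, so again 23/69/96%.

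**RR versus AR in nonusers.** 600 against 600: SE = √(2/600) = 0.0577. Power is 41% at 0.10 SD and 93% at 0.20 SD, with a 95% confidence half-width of 0.11 SD.

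**Number of groups.** Section III.B says eight conditions, IV.D says six, and 2800/400 implies seven. With eight groups of 350, the interaction SE is √(4/525) = 0.0873 and power at 0.10/0.20/0.30 SD is 21/63/93%. If the six conditions in IV.D were the whole design, there would be no control comparison.

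**The secondary matter: RR versus AR overall.** The pooled contrast is 1200 against 1200, SE = √(2/1200) = 0.0408. If it is the first Holm step among three or four planned tests, the critical values are 2.394 and 2.498. The plan's route (F gate at 0.05, then Holm over 21 pairs, control at the AR mean) was simulated, counting success if any matched RR-over-AR pair is significant.

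| True pattern | Pooled contrast | Plan's pairwise route |
|---|---|---|
| Equal RR effect at all three efficacy levels, 0.10/0.15/0.20 SD | 48–52 / 88–90 / 99% | about 15 / 46 / 82% |
| RR effect at one efficacy level only, 0.20 SD | 19–22% | 43% |
| RR effect at one efficacy level only, 0.30 SD | 48–52% | 90% |

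In the last two rows the pooled contrast sees only a third of the effect (0.20/3 = 0.067 SD; 0.30/3 = 0.10 SD).

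**The case against.** The best defence is that Phase 2 is a message-selection experiment. It is sized to pick the best group, all-pairs tests serve that purpose, and the linear model could take a user-status term or a pooled contrast at any time because ever-use is prescreened (IV.D) and tobacco use is measured at baseline (B.2). All of that is true. It makes this a gap in specification, not in design or data. It does not supply the user-type test that B.1 promises.

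On the RR-versus-AR contrast the defence has more force. A reader might infer that the pairwise plan is simply a weak test of the factorial hypothesis. The documents do not support that in general: in a 2x3 design threat and efficacy may interact, and if RR works at one efficacy level only, the pairwise tests are the stronger route. VI.D also says, after noting reported effect sizes of 2 or more, that "we do not consider smaller differences to be of interest". That sits badly with sizing on 0.1 SD, but if it governs, power at small effects matters little. This part is therefore optional.

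A reader might also take RR versus AR among nonusers as the test of harm. It cannot be that alone: AR messages lowering intentions while RR messages do nothing would give the same contrast. The control comparison is needed.

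Finally, Phase 2 data may already exist. Aim 2 is built from Aim 1's most effective messages, and some Aim 2 participants are being asked to re-consent. The documents do not say whether the Phase 2 data have been examined.

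**Conclusion.** The main point stands on the text. B.1 commits Phase 2 to a user-type comparison and allocates half the sample to it; VI.D contains no analysis of it, and III.B still describes a sample without nonusers. Under the stated model a nonuser-only effect is halved and cannot be located. The halving follows from the 50/50 split alone.

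The power figures rest on the assumptions listed above. They show a question that can be answered for effects of about 0.2 to 0.3 SD and only poorly at 0.10 SD. Estimates with confidence intervals will therefore be more informative than the interaction p-value.

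The missing RR-versus-AR contrast is secondary. The gain from adding it is real if the RR effect is similar across efficacy levels, and at no covariate gain a gap remains even at 0.20 SD (99% against about 82%). It reverses if the effect is confined to one level.

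**What to change.** In VI.D:

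1. Add baseline user status as a covariate and a threat-by-user-status interaction.
2. Report RR versus AR and RR versus control, with confidence intervals, separately in users and nonusers. Name intentions to use tobacco or ENDS as the key nonuser outcome.
3. Analyse quit and switch intentions in users only.
4. State the power of these comparisons, including that it is modest for the interaction and for RR versus control in nonusers.

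Reconcile the III.B description of the sample with B.1, and settle the number of groups, since the control comparison depends on it.

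Optionally, add a planned RR-versus-AR contrast averaged over efficacy together with a threat-by-efficacy test. Keep the all-pairs tests for message selection, and state how error is controlled across the two families.

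The cost is analysis text and code; no new data are needed. If Phase 2 data have already been examined, label all of these additions post hoc.

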**Table 2. Message sets for formative message testing in a 2x3 between subjects experiment (Aim 1 Phase 2)**

		THREAT	
		ABSOLUTE RISK (AR)	RELATIVE RISK (RR)
EFFICACY	Quit only (Q)	Set 1: AR/Q (n = 8)	Set 2: RR/Q (n = 8)
	Switch only (S)	Set 3: AR/S (n = 8)	Set 4: RR/S (n = 8)
	Combined quit + switch (QS)	Set 4: AR/QS (n = 8)	Set 6: RR/QS (n = 8)

**Aim 1, Phase 1: Study 2 –ONLINE RATING SURVEY:** In Phase 1, Study 2 we will conduct an online survey to quantitatively examine young adults’ perceptions of 8 absolute risk and 8 relative risk anti-tobacco messages and quit/switch efficacy statements. To reduce participant burden, each participant will view a random sample of messages as follows: n = 5 absolute and relative risk anti-tobacco messages (of N = 24), and n = 3 (of N = 12) efficacy messages. They will be asked to rate absolute and relative risk antitobacco messages and quit/switch efficacy statements for perceived message effectiveness, likeability, and reactance.

**Aim 1, Phase 1: Study 3 –IN-DEPTH INTERVIEWS:** Interviewees will be asked to share their reactions to the 24 textual anti-tobacco messages tested in Study 2. Specifically, interviewees will be asked to rate their top 5 (of N =12) absolute risk and top 5 (of N =12) relative risk antitobacco messages. We will then qualitatively explore their rationale for their top 5 selected messages.

**Aim 1, Phase 2: ONLINE FACTORIAL EXPERIMENT** (NCT05393869): Using a 2x3 factorial experiment (Table 2), plus control group design we will test the influence of AR and RR message framing on perceived effectiveness, tobacco risk perceptions, and behavioral intentions in young adult ever polytobacco users. Participants will be randomized to one of 8 conditions, including 6 experimental sets of AR and RR anti-tobacco messages (Table 3) and a control set of AR or RR regulatory control messages. We will present 8 messages within each experimental and control set. An expert panel of scientists, selected and invited by the mentoring team, will review all messages, which we will further refine based on expert feedback prior to testing in Aim 1, Phase 2 (NCT05393869).

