#### **D. Aim 1, Phase 2: ONLINE FACTORIAL EXPERIMENT (NCT05393869) Procedures**

Prescreening and consent. Participants will be recruited via Prolific, an online platform open to participants who are compensated for completing surveys and online behavioral experiments. Prolific is an efficient online recruitment platform, ideal for pilot studies, as it can deliver a high number of participants, per day, at low cost (recommended, minimum \$0.175 per minute of survey participation time). Data quality provided by Prolific samples is high and comparable to that from traditional college student samples . Prolific offers access to over 38,000 United States nationals. Prolific samples are young; approximately 1/3 of the Prolific population reports ages < 35 years old, which makes Prolific an ideal pool for recruiting young adult survey participants. Prolific is also a viable method for recruiting hard-to-reach populations for survey research, including LGBT populations .

Prescreening will be conducted via Prolific. Prolific is able to segment our population of interest for age (18-35 years) and currently residing the United States. It can also help us track gender and sexual orientation in order to balance recruitment. We are able to add in a custom pre-screening question to assess for prior history of ever nicotine and tobacco use.

Participants who meet eligibility criteria will be directed to an online survey administered via Qualtrics. Consent will be completed online prior to the Qualtrics survey.

Qualtrics survey procedures. Following online consent, participants will be directed to complete a survey that includes questions assessing tobacco use, including exposure to tobacco related advertising, coupons, and discounts; harms perceptions and tobacco-related behavioral intentions (i.e., quit, switch); and online/social media use questions.

Participants will answer baseline survey questions before random assignment to 1 of 6 experimental conditions in the 2 (Threat: Absolute/Relative Risk) X 3 (Efficacy: Quit, Switch, Quit plus Switch) design. Participants will view 8 randomly-ordered, anti-tobacco messages within their assigned condition; they will rate each message for perceived effectiveness and reactance. After viewing all messages, participants will complete a post-survey and receive \$0.225/minute (estimated \$4.50) via Prolific for participating.

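### The 75% that justifies 400 per group in Aim 1 Phase 2 is the chance that the highest mean belongs to the best group, not the power of the planned F-test and Holm comparisons, for which no power is stated

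*Combined protocol and SAP*

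**What the plan says.** The sample size paragraph of Section VI.D takes 400 analysed participants in each group and claims that this number "will allow us to detect the best message in terms of risk perception score with 75% probability", provided "the mean score in the best group is at least 0.1 standard deviations better than the mean score in the second best group". It cites reference 126, a text on statistical selection, screening and multiple comparisons. No other justification is given for the analytic total of "N = 2800 participants (n = 400 participants per experimental or control group").

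The analysis paragraph just above it fits linear regression models with covariates. It then says: "We will conduct overall F-tests to determine if there is an effect of condition in each model". The next sentence reads: "If so, pairwise t-tests will be conducted, and Holm's procedure will be used to control Type I error rate". The section gives no rule for naming a best set, no alpha, and no power for the F-test or the pairwise tests.

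Two other statements bear on the point. The number of groups differs by place. Section III.B says "Participants will be randomized to one of 8 conditions, including 6 experimental sets of AR and RR anti-tobacco messages", Section IV.D says "random assignment to 1 of 6 experimental conditions in the 2 (Threat: Absolute/Relative Risk) X 3 (Efficacy: Quit, Switch, Quit plus Switch) design", and VI.D implies 2800 / 400 = 7. Section III.C says that Aim 2 will start from the most effective Aim 1 messages, 12 relative-risk and 12 absolute-risk, without saying how they are chosen.

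**The concern.** A reader will take the 75% as the chance that the trial's own analysis identifies the best message set. It is not. A selection probability describes a procedure that always names a winner: take the highest sample mean. A gated testing procedure names a winner only when the data clear significance thresholds, and at a 0.1 SD lead with 400 per group they seldom do.

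Two things are at stake. The only figure supporting 2,800 analysed participants does not describe the analysis that will be run. And the Aim 1 hypotheses, which compare framings and efficacy statements, rest on tests whose sensitivity is not stated anywhere.

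**Working it through.** **Inputs.** From VI.D: n = 400 per group and a lead of δ = 0.1 SD. The number of groups k is 6, 7 or 8, as above. Assumed, because Phase 2 does not state it: alpha 0.05, two-sided. SD means the residual SD of the model unless noted.

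**1. Reproduce the 75%.** In the least favourable case (best group δ above all the others, which are tied), the chance that the best group has the highest sample mean is

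P = ∫ φ(x) · Φ(x + δ√n)^(k−1) dx, with δ√n = 0.1 × √400 = 2.

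| k | P(highest mean is truly best) | n per group for exactly 75% |
|---|---|---|
| 6 | 75.8% | 388 |
| 7 | 73.3% | 426 |
| 8 | 71.1% | 459 |

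The stated 75% is reproduced within two points for 6 or 7 groups, so it is a selection probability.

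**2. Planned analysis, same configuration.** The noncentrality of the overall F is nδ²(k−1)/k, that is 4 × (k−1)/k = 3.33, 3.43 and 3.50 for k = 6, 7 and 8. The Holm results come from simulation (at least 200,000 trials per case): F at 0.05, then all 15, 21 or 28 pairwise pooled-SD t-tests with step-down Holm.

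| Event | k = 6 | k = 7 | k = 8 |
|---|---|---|---|
| F-test significant | 24% | 23% | 22% |
| F significant and best group has the top mean | 22% | 20% | 19% |
| Best group Holm-superior to at least one rival | 19% | 17% | 16% |
| Best group Holm-superior to every rival | 0.37% | 0.16% | 0.08% |

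Independent runs agree within about a point on the first three rows and stay under 0.4% on the last. At alpha 0.10 the last row is 0.78%, 0.39% and 0.18%. For one pair at 0.1 SD, power is 29% unadjusted and 5.2% at 0.05/21.

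**3. Detectable pairwise difference.** For 80% power at the first Holm step with m pairs: (z(1 − 0.05/(2m)) + 0.842) × √(2/400).

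- m = 15: (2.935 + 0.842) × 0.0707 = 0.267 SD
- m = 21: (3.038 + 0.842) × 0.0707 = 0.274 SD
- m = 28: (3.124 + 0.842) × 0.0707 = 0.280 SD

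**4. Sensitivity of superiority over every rival (k = 6 / 7 / 8).**

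- If the 0.1 is in raw SD and covariates explain 25% of the variance: 0.8% / 0.4% / 0.2%. At 50%: 2.3% / 1.4% / 0.7%. At 70%: 10% / 6% / 4%. The plan gives no R-squared. Adjustment also raises the selection probability, to about 89-91% at 50%.
- If only the second best is close and the rest lie far below: 10% / 8% / 6%, while the selection probability rises to about 92%.
- If control lies 0.1, 0.2 or 0.3 SD below five tied sets (k = 7), the F-test passes in 53%, 93% and over 99% of trials. Superiority over every rival stays under 1%, and the selection probability stays at about 73-76%.
- With larger leads over tied rivals (k = 7): 11% at 0.2 SD, 68% at 0.3 SD, 98% at 0.4 SD, and about 100% at 2 SD.

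**The case against.** Four points can be made for the plan.

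- **Carry-forward is not tied to the tests.** A reader might infer that a non-significant F-test would leave nothing to take into Aim 2. The documents do not support that. Only the pairwise tests depend on the F-test, and nothing in Section III.C or VI.D makes the choice of messages depend on either. What stands is that the choice follows no written rule.
- **The all-tied case is a lower bound, not a forecast.** A reader might also infer that the analysis will usually stop at the F-test. That fails once control lies somewhat below the message sets, as step 4 shows. But an F-test that passes because control is low does not say which set is best.
- **Under 1% is a strict reading.** It means significant superiority over every other group, a goal that the plan never sets. On the looser readings the figure is about 15-22% in the same configuration, still well short of 75%.
- **The plan may have larger effects in mind.** VI.D adds that effects of 2 or more are reported in the literature and that smaller ones are not of interest. No unit is given. If it is SD, the planned tests have essentially full power, but then the 0.1 SD lead in the preceding sentence cannot be the planning difference. This is a conflict to resolve, not a defence of the 75%.

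It is also fair that Aim 1 is described as formative, and that Holm's procedure is there to limit type I error in the pairwise tests.

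**Conclusion.** The point holds as a mismatch between the sizing statement and the analysis. The 75% is correct, within rounding for 6 or 7 groups, for choosing the highest mean. It is not a property of the F-test and Holm procedure, for which the plan gives neither alpha nor power. How large the gap is depends on what counts as detecting the best message, on where the other groups lie, on the variance explained by covariates and on the assumed alpha. Strict superiority over every rival stays at or below about 10% across the 0.1 SD cases examined, while the selection probability is 71% or more in each of them. This should be fixed. It does not invalidate the experiment and does not call for a larger sample.

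**What to change.** In Section VI.D:

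1. State what the 75% means, for example: *the group with the highest covariate-adjusted mean risk-perception score is truly the best with this probability if it leads the second best by 0.1 SD; the ranking is reported whatever the F-test shows.*
2. Settle the number of groups across III.B, IV.D and VI.D, and quote the probability for the number of groups actually ranked together.
3. Put the ranking in a form that fits Section III.C. A rule that carries forward one winning set would not do: by Table 2 a set holds 8 messages of a single framing, whereas Aim 2 takes 12 of each. Ranking within each framing is one option. The rule should say how 12 messages per framing follow from it, and the probability must be recomputed for that k.
4. State the alpha and the detectable difference for the F-test and Holm comparisons separately. If alpha is 0.05 two-sided, this is about 0.27-0.28 residual SD per pair for 80% power at the first Holm step.
5. Give the unit of the effect size of 2 and reconcile that sentence with the 0.1 SD lead.

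The cost is a few sentences and agreement on the number of groups; no new data or participants are needed. The downside is that the figure stated for the tests is less favourable than a 0.1 SD lead suggests.
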